3.3. Endpoints

3.3.1. Efficacy Endpoints

The efficacy data summary will include the following endpoints:

- 1) Change from baseline in metHb after the first dose of ProvayBlue™ infusion.
The primary efficacy will be the number (%) patients with $\geq 50\%$ reduction in metHb based on the first available posttreatment assessment.
 - The following are secondary endpoints to support the primary endpoint.
 - i. Change in metHb posttreatment over time
 - ii. Time when 50% reduction in metHb is observed for the first time.
- 2) Change from baseline in vital signs (blood pressure, respiratory rate, and heart rate) after the first dose of ProvayBlue™ infusion.
 - The secondary efficacy will be the number (%) of patients with concomitant normalization of vital signs within 2 hours, inclusive, after the end of infusion of the first dose of ProvayBlue™
 - Time (hours) when the first incidence of normal vital signs was observed in patients who had abnormal baseline vital signs
- 3) In addition, 13 prespecified clinical signs and symptoms associated with methemoglobinemia and their intensity (as National Cancer Institute Common Terminology Criteria for Adverse Events [NCI-CTCAE] grade) before and after ProvayBlue™ treatment are collected. The presence/absence of those signs and symptoms will be treated as an 'other' efficacy endpoint since decrease and/or resolution of those signs and symptoms may be considered supportive of efficacy.

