5.1.1. MetHb Level at 1-hour Post Dosing

The timing of postdosing metHb level assays is inconsistent in clinical practice and may not be obtained until hours after the conclusion of first dose infusion in the emergency department. It should be noted that, consistent with such practice, the Observational Study does not have a prespecified schedule for metHb postdosing collection. MetHb level at 1-hour postdosing will be derived using linear interpolation. This method will be referred to as backward linear interpolation if the first postdosing metHb was after 1 hour, or forward linear interpolation if the first postdosing metHb was before 1 hour. This method will be mathematically expressed as follows.

Step 1: calculate rate of metHb change per minutes)

$$= (\text{metHb_1} - \text{baseline}) / \text{time of metHb_1 in minutes}$$

Step 2:

$$\text{metHb_1hr} = \text{baseline} + 60 * [(\text{metHb_1} - \text{baseline}) / (\text{time of metHb_1 in minutes})]$$

where

- baseline = baseline metHb defined as the last metHb before the first dose of study drug)
- metHb_1 = first post treatment metHb observation
- constant (60) converted the time units from minutes to hours

For example, a patient has metHb of 74.40 at baseline and 15.70 at 70 minutes postdosing. The estimated metHb_1hr is 24.08571.

Percent change from baseline (PCHG) at 1-hour post dosing can be estimated as follows.

$$\text{PCHG (\%)} \text{ at 1-hour post dosing} = 100 * [(\text{metHb_1} - \text{baseline}) / \text{time of metHb_1 in minutes}] / \text{baseline}$$

The PCHG for the above example is -67.63%.

$$\text{PCHG at 1-hour} = 100 * \{ [60 * (15.7 - 74.4) / 70] / 74.4 \}$$

Due to the mathematical property of this derivation, a patient could never achieve 50% reduction at 1-hour post dosing if the first postdosing metHb was taken after 2 hours. Hence, this derivation will be applied only to those patients who had first postdosing metHb before 2 hours.

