5.1.2. Time When metHb Level Reached 50% Reduction

To estimate the time when a 50% reduction would be obtained, the following linear interpolation will be applied.

$T_{50} \text{ (minutes after first dose)} = (\text{baseline}/2) / [60 * (\text{baseline} - \text{metHb}_1) / \text{time of metHb}_1 \text{ in minutes}]$

T50 for the above example is 44 minutes.

$$T_{50} = (74/2) / \{ [(74.4 - 15.7) / 70] / 74.4 \} = 37.2 / 0.838571428 = 44.36$$

The units for T50 will be converted to hours by $T_{50} / 60$ in the dataset.

Due to the mathematical property of this derivation, a patient could never achieve 50% reduction at 1-hour post dosing if the first postdosing metHb was taken after 2 hours. Hence, this derivation will be applied only to those patients who had first postdosing metHb before 2 hours.

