5.1.3. Summary of metHb

The treatment effect on metHb will be evaluated based on change in metHb from baseline. Because of the wide range in assessment times, the summary table will include only 2 time points: Baseline (last metHb before treatment) and predicted metHb at 1-hour posttreatment. The table will provide descriptive statistics for the observed metHb level, change from baseline, and percent change from baseline, including sample size, mean, standard deviation, and 2-sided 95% confidence intervals for the mean, minimum, median, and maximum. Number (%) patients with $\geq 50\%$ metHb reduction 1 hour posttreatment will be identified. (Table 14.2.1.1). This table will also include predicted time when metHb 50% reduction would occur and time when the first metHb is obtained.

[figure not shown]
A second summary table (Table 14.2.1.2) will provide metHb level descriptive summary at baseline and metHb level of the first follow-up posttreatment for all patients in the efficacy analysis set. In this table, the level of metHb at the first follow-up and time when the first follow-up metHb is taken will be summarized.

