7. ABLE OF CONTENTS OF PLANNED DATA SUMMARIES

7.1. Summary Tables

Number	Type	Title	Analysis Set
14.1.1	Table	Patient Enrollment and Analysis Set and Post Treatment Follow-up Status	Enrolled Analysis Set
14.1.2.1	Table	Demographics and Baseline Characteristics	Safety Analysis Set - Primary Cases
14.1.2.2	Table	Demographics and Baseline Characteristics	Safety Analysis Set - All Patients
14.1.2.3	Table	Demographics and Baseline Characteristics	Efficacy Analysis Set
14.2.1.1	Table	Predicted MetHb Level 1 Hour Post First Infusion in Patients with First MetHb Drawn Within 2 Hours of Dosing	Efficacy Analysis Set
14.2.1.2	Table	Summary of 1st Follow-up MetHb Level Regardless When the Assessment Was Taken	Efficacy Analysis Set
14.2.1.3	Figure	Individual Profile of Change from Baseline in MetHb Before and After Treatment	Safety Analysis Set - All Patients
14.2.2.1	Table	Summary of Vital Signs at Baseline and Within 2 Hours Post First Infusion	Efficacy Analysis Set
14.2.2.2	Figure	Individual Profile of Change from Baseline in Vital Signs Before and After Treatment	Safety Analysis Set - All Patients
14.2.3.1	Table	Summary of Methemoglobinemia Signs and Symptoms Before and After Treatment	Efficacy Analysis Set
14.2.3.2	Figure	Scatter Plots Showing Individual Profile of Methemoglobinemia Signs and Symptoms Before and After Treatment	Efficacy Analysis Set
14.3.1.1	Table	Study Drug Infusions	Safety Analysis Set - Primary Cases
14.3.1.2	Table	Study Drug Infusions	Safety Analysis Set - All Patients
14.3.2.1.1	Table	Topline Summary of Treatment Emergent Adverse Event	Safety Analysis Set - Primary Cases
14.3.2.1.2	Table	Topline Summary of Treatment Emergent Adverse Event	Safety Analysis Set - All Patients
14.3.2.2.1	Table	All TEAE by Preferred Term Displayed the Most Commonly Reported Event First	Safety Analysis Set - Primary Cases
14.3.2.2.2	Table	All TEAE by Preferred Term Displayed the Most Commonly Reported Event First	Safety Analysis Set - All Patients
14.3.2.3.1	Table	All TEAE by SOC and Preferred Term	Safety Analysis Set - Primary Cases
14.3.2.3.2	Table	All TEAE by SOC and Preferred Term	Safety Analysis Set - All Patients
14.3.2.4.1	Table	All TEAE by SOC, Preferred Term and Intensity	Safety Analysis Set - Primary Cases
14.3.2.4.2	Table	All TEAE by SOC, Preferred Term and Intensity	Safety Analysis Set - All Patients
14.3.2.5.1	Table	All TEAE by SOC, Preferred Term and Relationship to Study Drug	Safety Analysis Set - Primary Cases

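### The SAP names the time a 50% metHb fall is first observed as a secondary endpoint, but derives and tabulates only a predicted T50 in patients first sampled before 2 hours

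*SAP*

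**What the plan says.** SAP 3.3.1 sets out what the efficacy summary will contain. Among the endpoints supporting the primary metHb endpoint it lists "Time when 50% reduction in metHb is observed for the first time".

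The only time-to-50% derivation is in SAP 5.1.2: "To estimate the time when a 50% reduction would be obtained, the following linear interpolation will be applied". It uses baseline and a single post-dose value, defined in SAP 5.1.1 as "metHb_1 = first post treatment metHb observation". Section 5.1.1 allows the line to run past that sample, as "forward linear interpolation if the first postdosing metHb was before 1 hour", and T50 uses the same line. Section 5.1.2 then narrows the population: "this derivation will be applied only to those patients who had first postdosing metHb before 2 hours".

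On reporting, SAP 5.1.3 says of Table 14.2.1.1: "This table will also include predicted time when metHb 50% reduction would occur and time when the first metHb is obtained". The title of that table in SAP 7.1 is "Predicted MetHb Level 1 Hour Post First Infusion in Patients with First MetHb Drawn Within 2 Hours of Dosing". Table 14.2.1.2 covers the whole efficacy set but holds only the first follow-up level and the time it was taken. No other summary table in SAP 7.1 covers post-dose metHb. At patient level, SAP 5 promises listings for every efficacy endpoint, and SAP 5.1.4 plots every metHb assessment.

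**The concern.** An observed time and a predicted time are different quantities. Followed exactly, the plan never summarises the endpoint it names. A reader of the tables sees a time to 50% reduction that rests on an assumed straight line and one post-dose sample. It covers only patients selected by when they happened to be sampled, and it takes no account of later samples that may show directly when, or whether, the level had halved.

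This bears on the purpose of the report. Time to reduction is the first efficacy endpoint that SAP Table 1 lists for the Observational Study. That study supplied 24 of the 31 enrolled patients (7 + 24, SAP 1), and the pooled report is meant to satisfy the post-marketing requirement. The SAP also expects dapsone to keep producing metHb during the acute phase (3.7.2). A straight line from one early sample is least safe in those patients.

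**Working it through.** **1. The SAP's own example (5.1.1 and 5.1.2).** Inputs: baseline 74.40; first post-dose value 15.70 at 70 min.

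- T50 = (baseline/2) / [(baseline − first value)/time] = 37.2 / [(74.4 − 15.7)/70] = 37.2/0.838571 = 44.36 min. This matches the SAP's figure.
- It matches only without the factor 60 in the printed general formula. With that factor the result is 0.739, which is in hours but labelled minutes.
- Observed fall at 70 min: (74.4 − 15.7)/74.4 = 78.9%. The endpoint as named is therefore 70 min, which is 70 − 44.36 = 25.6 min later than the T50 that would be tabulated.

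Here the two differ but do not conflict: 44 min lies between baseline and the first sample, where the halving must have occurred.

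**2. When they conflict.** Let t be the first sample time and f the fractional fall at that sample. Then T50 = t/(2f).

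- If f is 0.5 or more, T50 is at or before t. It is an interpolation and cannot be later than the observed time.
- If f is below 0.5, T50 is after t. It is an extrapolation, and later samples can refute it.

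Illustrations with assumed values, baseline 40 (50% level = 20):

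| Samples | T50 | First observed 50% fall |
|---|---|---|
| 36 at 20 min, 16 at 60 min | 20/(4/20) = 100 min | 60 min (60% fall) |
| 30 at 30 min, 26 at 60 min, 18 at 180 min | 20/(10/30) = 60 min | 180 min (35% fall at 60 min) |
| 30 at 30 min, 28 at 60 min, 27 at 120 min | 20/(10/30) = 60 min | never |
| 42 at 20 min, 15 at 60 min | 20/(−2/20) = −200 min | 60 min |

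The error runs in both directions. If the first value equals baseline, T50 is undefined. The SAP has no rule for a first value at or above baseline.

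**3. The 2-hour limit.** The reason given in 5.1.2 is that the line cannot show a 50% fall at 1 hour when the first sample comes after 2 hours. That is true of the 1-hour value. It does not stop T50 from being calculated.

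- Since f cannot exceed 1, T50 is at least t/2. For any t above 120 min with a fall, T50 is above 60 min (t = 150 gives at least 75 min; t = 240 gives at least 120 min).
- The limit therefore removes only T50 values above 60 min and keeps every value below. The share of reported T50 values at or below 60 min can only rise or stay the same.
- Example (assumed): baseline 40, first sample 5 at 150 min. An 87.5% fall is observed at 150 min, and T50 would be 20/(35/150) = 85.7 min. The patient has no time-to-50% entry in any table.

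**The case against.** The case for leaving the plan alone has real substance.

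- **The observed data are not hidden.** Every metHb value is plotted by patient, and listings are promised for all efficacy endpoints, with observed and derived values. A reader could work out the observed time patient by patient. This stands. A reader might infer that the report discards all later samples; the documents do not support that. Later samples are left out of the T50 formula and the summary tables, not out of the report.
- **The report is mainly narrative.** The SAP plans patient narratives, limited statistics and no inference, in at most 31 patients and fewer in the efficacy set. This lowers the stakes but does not remove an endpoint that 3.3.1 says the summary will include.
- **Table 14.2.1.2 partly fills the gap.** Where the first sample already shows a 50% fall, its time is the first observed time. But the table summarises first-sample times for everyone, without separating those who had reached 50%.
- **Conflict may be uncommon.** It needs a first sample with less than a 50% fall. Protocol 6.5 reports a 50% fall within 1 hour in 15/17 + 12/13 + 16/17 = 43 of 47 historical patients. Those figures do not describe first samples, so the frequency here is unknown.
- **The SAP is open about the method.** It calls T50 estimated and predicted. That makes the table honest, but it still reports a quantity other than the named endpoint.

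**Conclusion.** The point holds for the derived parameter and the summary tables. The endpoint in SAP 3.3.1 has no derivation and no table. Its stand-in is a different quantity, in a subset chosen for a reason that belongs to another parameter.

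In the SAP's own example the difference is 25.6 min. The contradictions in the table above use assumed values. They show what the rule permits, not how often it happens.

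A reader might infer that T50 always flatters the drug or always conflicts with the data. Neither follows. T50 is never later than the observed time when the first sample shows at least a 50% fall; otherwise it can err either way, and 100 min predicted against 60 min observed is unfavourable to the drug. The 2-hour limit does favour shorter times, in the sense that it drops only values above 60 min. A mean or median need not fall in every dataset, because long extrapolated values from early samples are kept.

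This is a secondary, descriptive endpoint. The change is worth making before the tables are produced; it does not undermine the primary endpoint, which SAP 3.3.1 bases on the first available post-treatment value.

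**What to change.** For every efficacy-set patient with timed samples, derive from all post-dose metHb values and tabulate:

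- the first observed time with at least a 50% reduction from baseline;
- the last earlier sample time without it, so that the interval containing the event is visible;
- the number of patients in whom it was never observed.

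Flag or separate times reached only after a second or later dose: the endpoint concerns the first dose, and Protocol 8.1 allows a repeat dose 1 hour after it. Flag patients whose infusion stop time was imputed under SAP 3.3.2, since their relative times depend on it.

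Keep T50 as a labelled supportive estimate, computed only when samples bracket the 50% level. This also removes negative and undefined values at a first sample at or above baseline. Print its formula so that it returns the 44.36 min of the example.

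The cost is a little more programming. Some patients will have wide intervals or missing times. The SAP does not show that every sample time is available: only selected Interventional Study data are entered (3.1), and procedure times not recorded on the paper CRF must be queried (2.2.1, PVP-2016003). The table should therefore state how many patients could not be timed.

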3.3.2. Relative Time of Efficacy Endpoints

A relative time frame will be used to display and to summarize efficacy assessments.

The stop time of the first ProvayBlue™ infusion will be used to derive relative time (hours) for each post infusion metHb and vital signs assessment. After all efforts are made to ensure the capture of infusion start and stop time, when the stop time is missing, the following imputation rule will be used to impute the missing stop time.

Missing stop time will be imputed with the median infusion duration of the efficacy population. Mathematically, this imputation rule can be expressed as

$$\text{Stop time} = \text{start time} + \text{median infusion duration}$$

Where the median infusion duration is derived from all patients in the efficacy population.

Relative time of an assessment (hours) = Time of assessment – Time of stop time of 1st Infusion.

3.3.3. Safety Endpoints

The following safety endpoints will be summarized:

- Prevalence and nature of treatment-emergent adverse events (TEAEs), defined as all AEs with onset date after the first dose of ProvayBlue™ infusion and within 10 days of the last dose of ProvayBlue™ infusion.
- Results of clinical laboratory tests before and after ProvayBlue™ treatment.
- Results of ECG before and after ProvayBlue™ treatment.

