15.3.3. Recording and Reporting of Adverse Events (AEs)

All AEs, as defined above, encountered during the clinical study as well as any **SAEs** (see Section 15.3.2) will be reported in the appropriate section of the CRF. Information will include the following:

- Duration of the AE (onset date and time and resolution date);
- Relationship to ProvayBlueTM (refer to Section 15.3.3.5);
- Time relationship to ProvayBlueTM dosing time;
- Assessment of whether AE is an infusion site reaction;
- Severity (refer to Section 15.3.3.6);
- Outcome of the AE;
- Concomitant treatment dispensed (or other action taken);
- Action taken with respect to the ProvayBlueTM.

If an AE increases in severity it will be recorded as a new record with the same AE identifier.

AE data should be obtained through observation of the patient, from any information volunteered by the patient (and the patient's parent[s]/legal guardian[s]) and through patient (and the patient's parent[s]/legal guardian[s]) questioning. The patient may be asked "Do you have any health problems?" or "Have you had any health problems since your last site visit?"

Refer to Section 15.3.3.9 for guidance relating to reporting of suspected, unexpected serious adverse reactions (SUSARs) to regulatory agencies.

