15.3.3.1. Adverse Event (AE) Reporting Period

ALL AEs or the worsening of any ongoing events which occur from PICD signature or the start of ProvayBlueTM treatment (whichever occurs sooner) up to 10 to 15 days after the last administration of ProvayBlueTM will be recorded in the CRF. All ongoing AEs and SAEs will be followed up until resolution, until the condition stabilizes, until the event is otherwise explained or until the patient is lost to follow up.

All AEs experienced by a patient, irrespective of the suspected causality, will be monitored until the event has resolved, any abnormal laboratory values have returned to baseline or stabilized at a level acceptable to the Investigator and Medical Monitor, until there is a satisfactory explanation for the changes observed, or until the patient is lost to follow-up.

Any untoward event that occurs after the AE reporting period but which the Investigator assesses as possibly related to ProvayBlueTM should also be reported as an AE or SAE.

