2.2.1. PVP-2016003

Protocol PVP-2016003 is an open-label, uncontrolled Phase 4 Interventional Study of patients who present in hospital/urgent care setting with acquired methemoglobinemia. The population may include pediatric and adult patients (males and females of all ages are included). Eligible patients will receive a single dose of study drug (typically 1 mg/kg of ProvayBlue™) treatment to treat acquired methemoglobinemia resulting in a direct health benefit. Patients will be followed post treatment; safety, efficacy, and PK data will be collected following a predefined data collection schedule (Table 2).

To create a harmonized electronic database, data collected from this study will be entered into the electronic data collection system used for the Observational Study, and the absolute dates of service recorded in this study will be converted to safe-harbor compliant “study days” before data are entered into the database for analyses. In instances where a specific procedure/data collection time was not initially recorded on the paper CRF, a data query will be generated to obtain the specific time from the site. All patients from this protocol are considered as Primary cases.

The original CRFs for Protocol PVP-2016003 requested posttreatment AE tracking, but the Study Procedure Chart indicates that AEs are tracked pretreatment. To be consistent with the Observational Study, any AEs collected prior to study drug treatment will be identified as NOT treatment-emergent events. Non-treatment-emergent AEs will be included in the data listing but will be excluded from data summary (see Section 6.2 for additional details).

Table 2: Study PVP-2016003 Procedures

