6.2. Adverse Events

Adverse events reported after the first dose of ProvayBlue™ infusion start time and within 10 days after the last dose of ProvayBlue™ infusion will be considered treatment-emergent adverse events (TEAEs). Any AEs that do not have onset time will be included as TEAEs if reported. Patients who did not have any AEs will be verified via source documentation.

The Medical Dictionary for Regulatory Activities (Version 23) will be used to classify all AEs with respect to system organ class and preferred term. All adverse events will be listed.

The following summary tables will be produced for the TEAEs. All data summaries will provide number (%) patients as well as total number of events in each category by patient group. Each summary will be produced in 2 sets: one includes the Primary cases and one includes all patients in the safety analysis set.

1. a topline summary of TEAEs (**Table 14.3.2.1.1**, **Table 14.3.2.1.2**)
2. a summary table by preferred term in descending order of total incidence (**Table 14.3.2.2.1**, **Table 14.3.2.2.2**)
3. a summary table by system organ class and preferred term (**Table 14.3.2.3.1**, **Table 14.3.2.3.2**)
4. a detailed summary table by system organ class, preferred term and severity (**Table 14.3.2.4.1**, **Table 14.3.2.4.2**)
5. a detailed summary table by system organ class, preferred term and relationship (**Table 14.3.2.5.1**, **Table 14.3.2.5.2**)
6. a table of serious TEAEs by system organ class and preferred term (**Table 14.3.2.6.1**, **Table 14.3.2.6.2**)

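### The SAP's two TEAE definitions differ and neither covers worsening, so an event recorded between consent and infusion that then worsens can be missing from every adverse-event table

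*SAP*

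**What the plan says.** - **SAP 3.3.3 (Safety Endpoints)** goes by onset. TEAEs are "defined as all AEs with onset date after the first dose of ProvayBlue™ infusion", up to 10 days from the last dose.
- **SAP 6.2 (Adverse Events)** goes by reporting: "Adverse events reported after the first dose of ProvayBlue™ infusion start time and within 10 days after the last dose". It adds a default for incomplete records: "Any AEs that do not have onset time will be included as TEAEs if reported". Every adverse-event summary that it plans is restricted to TEAEs.
- **SAP 2.2.1 (under PVP-2016003)** states that "any AEs collected prior to study drug treatment will be identified as NOT treatment-emergent events". It continues: "Non-treatment-emergent AEs will be included in the data listing but will be excluded from data summary". It refers to 6.2 for details.
- **Protocol 15.3.3.1** requires the CRF to hold "ALL AEs or the worsening of any ongoing events which occur from PICD signature", or from the start of treatment if that comes sooner.
- **Protocol 15.3.3** gives the recording rule: "If an AE increases in severity it will be recorded as a new record with the same AE identifier". It also asks for onset date and time, and severity.
- **Protocol 15.3.1** treats worsening of a pre-existing condition as an AE in its own right.
- **Protocol 16.5** planned to show all AEs in the summary tables, but SAP section 1 gives the SAP precedence over the protocol's statistical section.

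**The concern.** The protocol makes sites capture worsening, and the SAP has no rule that carries it into a table. A reaction that aggravates an event already present is something a safety summary should show. Any such omission works in one direction only: it lowers the TEAE, severity and serious-event counts.

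The rules also sit oddly together. An AE with no onset time is tabulated by default, while a fully timed AE that began before the infusion and became severe after it may not be. The report answers a post-marketing requirement and pools few patients, so a single event is visible in the percentages.

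**Working it through.** The plan states no figure to reproduce. The check compares the texts and makes two small counts.

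**1. Tables affected.** SAP 6.2 lists 6 summary types, each produced for Primary cases and for all patients: 6 × 2 = 12 tables (14.3.2.1.1 to 14.3.2.6.2 in SAP 7.1). All 12 are limited to TEAEs. An event classed as non-TEAE is in none of them and remains in Listing 16.2.10.

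**2. Each rule applied to the possible situations.**

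| Situation | 3.3.3 (onset) | 6.2 (reported) | 2.2.1 (collected before treatment) | Result |
|---|---|---|---|---|
| A. AE starts between consent and infusion and worsens after; new record keeps the first onset | Not a TEAE | Unclear: the event was reported before, the new record after | Excluded if the event is taken as one AE | Can be absent from all 12 tables |
| B. As A, but new record dated at the increase | TEAE | TEAE | First record excluded, new record not | Tabulated |
| C. AE starts and worsens after infusion | TEAE | TEAE | Does not apply | Tabulated; two records could count as two events |
| D. Symptom predates consent; its worsening after infusion is reported as an AE | Normally a TEAE, since the AE is the worsening | TEAE | Does not apply | Tabulated |
| E. Patient treated before consent | No AE recorded before infusion | Same | Does not apply | Not exposed |

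Only row A loses information. Rows A and B differ in one fact, the onset carried by the severity-increase record, and neither document states it. In row C the number of patients is unaffected; only the total number of events could be inflated.

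**3. Whether the window exists.** Row A needs an AE recorded after consent and before the first infusion. Protocol 15.3.3.1 opens collection at consent if that is earlier. Protocol 15.3, section 12.1 and note s of the flow chart start it at treatment. SAP 2.2.1 itself remarks that the CRFs asked for post-treatment tracking while the procedures chart indicates tracking before treatment. The number of exposed patients cannot be derived and may be zero.

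**4. Size.** SAP section 1 gives 7 interventional and 24 registry patients: 7 + 24 = 31. One patient who moves from no TEAE to any TEAE changes the all-patient incidence by 1/31 = 0.032, or 3.2 points. This needs all 31 to be in the safety set and the patient to have no other TEAE. The registry's split into Primary and Secondary cases is not given, so no step is computed for the Primary-case tables.

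**The case against.** The strongest reply is that the SAP does not classify by onset alone. A reader who stops at 3.3.3 might infer that it does, but 6.2 is the operative adverse-event section and uses reporting, under which a severity record made after the infusion can qualify. That stands. It replaces a certain omission with two definitions that can disagree, and 2.2.1 still removes events collected before treatment.

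Second, a reader might infer that a worsened event is necessarily dropped. The documents do not support this. If the new record is dated at the increase, even 3.3.3 tabulates it.

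Third, dizziness, headache, dyspnea and syncope are both presenting symptoms (protocol Table 6-1) and reactions in the appended label, so they look like natural examples. Mostly they are not. Presenting symptoms normally predate consent, so their worsening is a new AE with a post-infusion start. They are also among the 13 signs and symptoms graded before and after treatment (SAP 3.3.1 and 5.3). This is a partial safeguard: those tables count presence rather than change in grade and use the efficacy set, although the individual plots do show grade.

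Fourth, the event is not lost. Listing 16.2.10 keeps it, and SAP section 4 plans patient narratives. With 31 patients, a reader of the listing could find it. That limits the harm but does not correct the tables.

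Finally, 1/7 = 14 points might be offered as the effect within the interventional study. It corresponds to no planned adverse-event table: the AE summaries are by causative-agent group and by Primary or all cases, and only disposition is specified by protocol.

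**Conclusion.** The point holds as a gap in the rules. The SAP has two differing TEAE definitions and no worsening clause. Together with the exclusion in 2.2.1, this allows a post-infusion worsening to be missing from all 12 tables when its record keeps the pre-infusion onset.

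The exposed group is small and of unknown size. Patients treated before consent are outside it, and no affected patient is shown to exist. For the 24 registry patients the AE recording rules are not in the documents, so exposure cannot be judged. The effect of one patient on all-patient TEAE incidence is 3.2 points under the two conditions in the working. A reader might infer that the reported safety profile is biased. The documents support only that the rules permit an omission in the favourable direction, with the event still listed.

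**What to change.** Use one TEAE definition in SAP 2.2.1, 3.3.3 and 6.2: *an AE with onset after the start of the first infusion and within 10 days of the last dose, or an AE present before the first infusion that increases in severity or becomes serious after that infusion starts.*

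Then add two handling rules:

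- A severity-increase record takes the date and time of the increase for TEAE classification.
- Each event is counted once per AE identifier, at its maximum post-infusion grade, so that a worsening is neither dropped nor counted twice.

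The cost is a few lines in the SAP and a flag in the AE dataset. For the interventional study, protocol 15.3.3 already asks for onset time, severity and the identifier, so no new data should be needed. For the registry, first check that linked severity records exist; if they do not, state how worsening will be identified. The downside is that TEAE counts may rise slightly.
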